13.5.1. Reporting of Pregnancy

If, following initiation of the investigational product, it is subsequently discovered that a study subject or a female partner of a male study participant is pregnant or may have been pregnant at the time of investigational product exposure, including during at least 6 half-lives after product administration, the investigational product will be permanently discontinued for the female study participant in an appropriate manner. Protocol required procedures for study discontinuation and follow-up must be performed on the subject unless contraindicated by pregnancy (e.g. x-ray studies). Other appropriate pregnancy follow-up procedures should be considered if indicated.

Pregnancies should be reported to Propharma but will not be considered as SAEs. They will be tracked to determine the final outcome of the fetus. Propharma Pregnancy Questionnaire and Outcome forms will be used for this function. If the pregnancy ends in an unfavorable manner (i.e., miscarriage, birth defect, etc.), the investigator is responsible for determining if the outcome met SAE criteria.

Follow-up information regarding the course of the pregnancy, including perinatal and neonatal outcome and, where applicable, offspring information must be reported on the Pregnancy Surveillance Form. Infants should be followed for a minimum of 8 weeks.

13.6. Other Safety Considerations

Any significant worsening noted during interim or final physical examinations, electrocardiograms, x-rays, and any other potential safety assessments, whether or not these procedures are required by the protocol, should also be recorded as a nonserious or serious AE, as appropriate, and reported accordingly.

14. STATISTICAL METHODS

14.1. Sample Size Determination

The sample size (estimated to be between 100 and 175 subjects) during dose escalation and expansion cannot be precisely determined but depends on the observed toxicity.

There are 6 cohorts of subjects in the escalation portion of the protocol where INT230-6 dosing is increased over 5 doses. These escalation cohorts are (A1, B1, EA, EC, EC2 and DEC).

There are potentially 4 fixed dose cohorts (EC3, DEC2, FEC and G) that use a maximum total fixed dose of INT230-6 of 175 mL for all 5 induction doses as well as a maintenance dose. In EC3, DEC2 and FEC expansion cohorts, 10-16 subjects will be treated at fixed INT230-6 doses in a tumor type, to provide additional safety information and preliminary assessment of tumor response within a disease indication. G cohort will be a combination of fixed dose INT230-6 with other molecules. With 16 subjects treated in an expansion cohort, at a fixed dose and tumor type the 90% confidence interval for an objective response rate would be (5.3% to 42%) if 3 (19%) subjects had a response, (9.0% to 48%) if 4 (25%) subjects had a response and (13.2% to 54.8%) if 5 (31%) subjects had a response.

14.2. Study populations

14.2.1. All Enrolled Population

All subjects who sign informed consent form will be included. Subject disposition will be tabulated using this data set.

14.2.2. All Treated Population

All subjects who receive at least 1 dose or any partial dose of INT230-6. This population will be used for safety analyses, and primary efficacy analyses.

14.2.3. Pharmacokinetic Data Set

All available concentration-time data from subjects who receive INT230-6 will be reported. All available derived PK parameter values will be included in the PK data set and reported, but only subjects with adequate PK profiles will be included in the summary statistics and statistical analysis. PK sampling has been eliminated in Amendment 6.

14.2.4. Response Evaluable Data Set

Response evaluable subjects will be defined as all subjects who receive at least one dose of INT230-6, have a baseline tumor assessment with measurable disease, and one of the following: 1) at least one on-treatment tumor evaluation, 2) clinical progression, or 3) death prior to the first on-treatment tumor evaluation.

14.2.5. Exploratory Biomarker (Immune Function and others) Data Set

All subjects who receive at least one dose of INT230-6 and have at least one measurement for a specific marker will be included in the data set for that marker. All treated subjects with at least one baseline measurement will be included in predictive analyses; treated subjects with baseline measurement and at least one on treatment measurement will be included in pharmacodynamic assessments. Blood biomarker sampling has been eliminated in Amendment 6.

14.2.6. **Retreatment Population**

For cohorts A1, B1, EA, EC, EC2, DEC, those subjects who have completed treatment and have not started any subsequent anti-cancer therapy were eligible for retreatment. Subjects who qualified for re-initiation of treatment were evaluated for safety and efficacy based on availability of data.

14.3. **Statistical Considerations**

Please refer to the Statistical Analysis Plan (SAP).

14.3.1. **Demographics and Baseline Characteristics**

Subject demographics and baseline characteristics including age, sex, race, ethnicity, weight, baseline disease diagnosis, and medical conditions will be summarized by dose level using descriptive statistics.

14.3.2. **Extent of Exposure**

The dose of INT230-6 taken by subjects will be summarized by total dose and number of tumors injected. Additional parameters will be summarized, such a reason for study drug interruption and number of tumors with drug exuded. A by-subject listing of treatment exposure will be generated.

Combination study drugs for cohorts 7 and higher will also be summarized. Details will be provided in the statistical analysis plan.

14.3.3. **Tumor Response.**

The primary efficacy endpoint of disease control rate (DCR), defined as the sum of complete, partial and stable disease responses divided by the total number of subjects in the efficacy population, will be determined per iRECIST criteria for fixed dose and expansion cohorts. DCR will be tabulated by overall and by tumor type. Exploratory analysis will be conducted by cohort, Phase 1 cohorts (monotherapy and PD-1), Phase 2 cohorts (monotherapy, PD-1 and CTLA-4), Phase 1 and 2 cohorts (monotherapy and PD-1), tumor types, study visit, number of INT230-6 doses, number of cycles of INT230-6 (i.e., retreatment), and number of prior lines of therapy. Since iRECIST methods were not implemented at the time of dose escalation, DCR for these cohorts will be analyzed per RECIST v1.1.

For DCR, exact binomial 95% confidence intervals will be determined by Clopper-Pearson method. Median time to response and duration of response will be summarized for those subjects with confirmed responses, using Kaplan-Meier method; Progression free survival (PFS) will be similarly summarized. Individual tumor measurements, tumor burden and % changes in tumor burden will be listed. Changes in tumor burden will be presented graphically.

14.3.4. **Concomitant Medication**

Concomitant medications will be coded using the World Health Organization Drug Dictionary (WHODD). Concomitant medications will be summarized. Tabulation will be made with respect to the proportion of subjects taking at least 1 concomitant medication for each preferred term during the study. A listing of concomitant medications by subject will be provided.

14.3.5. **Safety**

The primary objective is to assess the safety and tolerability of multiple intratumoral doses of INT230-6 in subjects with advanced or recurrent malignancies. This will be assessed by the rate of \geq grade 3 AEs

Protocol IT-01 Version Amendment 6

attributed to study drugs (INT230-6 and others per the appropriate protocol supplement), and study procedure, and not the underlying disease.

Safety Analyses:

All recorded adverse events will be listed and tabulated by system organ class, preferred term, and coded according to version 19.1 of Medical Dictionary for Regulatory Activities (MedDRA). The incidence of adverse events will be tabulated and reviewed for potential significance and clinical importance. Vital signs and clinical laboratory test results will be listed and summarized. Any significant physical examination (PE) findings and results of clinical laboratory tests will be listed. Electrocardiogram (ECG) listings will be evaluated by the investigator and abnormalities, if present, will be listed.

Adverse Events will be summarized for all reported data and by study period: a) up to and including 28 days post last dose of initial treatment, and b) from first dose of re-initiation of treatment, for subjects who re-initiate study therapy while in follow-up, up to 28 days post-dose of the last re-treatment dose. In order to better estimate MTD or toxicity frequency of some events of interest, logistic regression or constrained Bayesian estimation may be used to model frequency by INT230-6 dose level for each population arm or across population arms when combination of different population arms is deemed appropriate.

The following safety parameters will be evaluated:

Adverse Events

An Adverse Event (AE) is defined as any new untoward medical occurrence or worsening of a pre-existing medical condition in a subject or clinical investigation subject administered an investigational (medicinal) product and that does not necessarily have a causal relationship with this treatment. An AE can therefore be any unfavorable and unintended sign (including an abnormal laboratory finding, for example), symptom, or disease temporally associated with the use of investigational product, whether or not considered related to the investigational product. Adverse events can be spontaneously reported or elicited during open-ended questioning, examination, or evaluation of a subject. (In order to prevent reporting bias, subjects should not be questioned regarding the specific occurrence of one or more AEs.)

Following the subject's written consent to participate in the study, all SAEs, whether related or not related to study drug, must be collected, including those thought to be associated with protocol-specified procedures. All SAEs must be collected that occur within 28 days of discontinuation of dosing. The investigator should collect any SAE occurring after these time periods that is believed to be related to study drug or protocol-specified procedure. A SAE report should be completed for any event where doubt exists regarding its status of seriousness. If the investigator believes that a SAE is not related to study drug, but is potentially related to the conditions of the study (such as withdrawal of previous therapy, or a complication of a study procedure), the relationship should be specified in the narrative section of the SAE Report Form.

Adverse events will be coded using the Medical Dictionary for Regulatory Activities (MedDRA) to categorize a system organ class and a preferred term for each adverse event. The number of subjects who experienced at least 1 adverse event, study drug related adverse event, severe (Grade 3 or above) adverse event, serious adverse event, and the number of subjects withdrawn due to adverse events will be summarized. For each system organ class and preferred term, summaries will be made with respect to the number and proportion of subjects having at least 1 occurrence of an adverse event during the study, using the worst grade reported within a subject. The incidence of adverse events will be presented overall, by system organ class and preferred term, intensity (based on NCI CTCAE Version 4.03), and additional grouping by severity and relationship to study drug. Individual listings of adverse events will be provided.

DLTs and study drug-related Grade >2 adverse events will be listed individually.

Physical Examination

Abnormal PE findings with onset prior to first dose of study drug will be recorded as medical history. Any abnormal or clinically significant findings on or after dosing will be recorded as an adverse event. Clinical significance will be determined by the Principal Investigator at each site.

Individual medical/surgical history will be listed by subject. Individual abnormal or clinically significant PE findings after dosing will be recorded as an adverse event and listed separately with AEs.

Vital Signs

Vital sign measurements and change from baseline will be summarized. Vital signs include weight, systolic blood pressure (SBP), diastolic blood pressure (DBP), body mass index (BMI, derived), heart rate, oxygen saturation, and temperature. Individual vital sign measurements will be listed.

ECGs

ECG data will be read and interpreted locally. Summary statistics of ECG overall interpretation will be displayed. Per subject ECG test results at will be listed.

Abnormal clinically significant ECG findings on or after informed consent will be recorded as an adverse event and displayed with AEs.

Clinical Laboratory Tests

Clinical laboratory values will be summarized in SI units. Severity grades will be programmatically calculated using standard American Medical Association's (AMA) laboratory normal ranges [AMA Manual of Style, AMA 2009] and the quantitative NCI CTCAE 4.03 criteria (when available for a specific laboratory abnormality). Laboratory values considered to be normal by CTCAE criteria, meaning they do not qualify as Grade 1-4, will be assigned a severity grade of 0.

Summary statistics of numerical laboratory test results and changes of test results from baseline will be reported for hematology, coagulation, serum chemistry, and urinalysis at each scheduled time point. For values with categorical results, the frequency and percentage of each result category will be tabulated at each scheduled time point. Shift tables will also be included reporting change from baseline category (low, normal, high) to post-dose category (low, normal, high). Abnormal laboratory values that lead to a change in subject management or that are considered to be of clinical significance will be reported as an adverse event (serious adverse event if relevant) and summarized by SOC/PT and according to severity in the appropriate AE tables. Clinical significance will be determined by the Principal Investigator at each site.

Pregnancy test results will be displayed in a listing.

ECOG Performance Status

ECOG performance status will be summarized using descriptive statistics. ECOG performance status per subject during the trial will also be listed.

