Investigational product, dosage and mode of administration:

INT230-6 administered intratumorally, a fixed combination of cisplatin, vinblastine and SHAO

Duration of treatment:

In A1 and B1 cohorts, subjects received injections monthly for up to 5 doses of INT230-6 (4 months). In E cohorts, injections are given every 2 weeks for up to 5 doses. Cohorts EC3, DEC2, FEC and potentially GEC will utilize the once every 2 weeks dosing for 5 doses followed by maintenance dosing once every 9 weeks +/- 10 days until CR, PD or 2 years, whichever is first. Given the short half-life of the components of INT230-6, safety follow up post the last dose of treatment is 28 days for monotherapy cohorts. Subjects are followed regularly until progression and/or start of subsequent anti-cancer therapy. Afterwards subjects will transition to a less frequent survival follow up. The total expected duration of the study is 5 years.

Reference therapy, dosage and mode of administration:

NA

Criteria for evaluation:

Efficacy:

Since this is a locally administered product, it allows for multiple efficacy analyses. The primary efficacy measure will be disease control rate (CR+PR+SD) as assessed by iRECIST. Since immune system activation is expected from preclinical studies, the trial will collect samples from the peripheral blood and from tumors to look at markers of activation. Furthermore, observing tumor shrinkage in non-injected bystander tumors would also indicate potential immune activation. In order to take the whole picture into account, the exploratory endpoints will look at overall tumor response, time to progression and overall survival.

Safety:

Assessment of safety will be determined by ongoing review of clinical laboratory tests (blood and urine sampling for clinical laboratory parameters), pregnancy testing, Eastern Cooperative Oncology Group (ECOG) performance status, physical examination including vital sign measurements, any needed or completed electrocardiogram (ECG), and adverse events.

Pharmacokinetic:

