5.2.1. E. SUPERFICAL and/or DEEP TUMORS (cohort EC3) Monotherapy of INT230-6

This cohort has simplified the dosing to inject up to the 175mL total dose of INT230-6 into a subject's tumors at each treatment (5 total for induction) session. There is 1 mL of INT230-6 dosed for each 3 cc of tumor volume (1:3) ratio with an induction dosing of 1 doses every 2 weeks for 5 doses with maximum fixed total dose of 175 mL with a maintenance dose of the same maximum of 175 mL given Q9 weeks +/- 10 days. Each tumor should receive up to its

maximum dose to achieve the 1:3 target ratio. The total dose is to be divided up and injected into as many tumors as feasible, with the aim to treat as many visible tumors as possible 1 to 3 times during the course of the induction treatment. After the 5 doses, subjects continue to the maintenance phase where they can repeat injecting new lesions or previously injected lesions with up to 175mL once every 9 weeks. Treatment should continue until patient's tumors disappear (CR), confirmed progression (iCPD) or 2 years whichever is first.

5.2.2. DEC2 Cohorts. COMBINATION WITH ANTI-PD-1 agent(s): see Supplement A for details on each PD-1 agent.

DEC cohorts were initiated and are a combination of INT230-6 plus an anti-PD-1 therapy. The subject population (tumor types) and other details for this group of subjects is defined in Supplement A.

5.2.3. FEC Cohorts. COMBINATION WITH ANTI-CTLA4 agent(s): see Supplement B for protocol details for INT230-6 combinations with anti-CTLA-4 agent(s).

Cohort FEC was initiated and is a combination of INT230-6 plus an anti-CTLA4 therapy. The subject population (tumor types) and other details for this group of subjects is defined in Supplement B.

5.2.4. GEC Cohorts. Cohorts containing the letter “G” dose INT230-6 with agents other than PD-(L)1 or CTLA-4 antibodies.

The subject population (tumor types) and other details for this potential group of subjects will be defined in a future Supplement C.

Study Steering Committee

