9.3. Stopping Rules for Clinical Deterioration

Accumulating evidence indicates that the emergence of objective responses to agents that activate anti-tumor immune responses follows delayed kinetics of weeks or months, and can be preceded by initial apparent radiological progression, or appearance of new

tumors or some enlarging tumors while certain target tumors are regressing (“mixed response”). It is thus reasonable to allow for these possibilities and continue to treat the subject until progression is confirmed and found to be advancing and continuing at the next imaging assessment. These considerations should be balanced by clinical judgment as to whether the subject is clinically deteriorating and unlikely to receive any benefit from continued treatment. Such deterioration will be assessed to have occurred after a clinical event that, in the Investigator’s opinion, is attributable to disease progression, is unlikely to reverse with continued study treatment and therefore indicates that the subject is not benefiting from study treatment and cannot be managed by the addition of supportive care (such as bisphosphonates and/or bone directed radiotherapy, thoracentesis or paracentesis of accumulating effusions). The decision to continue or stop treatment should be discussed with the Sponsor Medical Monitor and will be documented in the study records.

Examples of events that may, in the Investigator’s opinion, indicate a lack of clinical benefit include, but are not limited to, the following:

- Performance status decrease of at least 2 points from baseline
- Skeletal related events defined by the following:
 - Pathologic bone fracture in the region of cancer involvement
 - Cancer related to bone surgery
 - Spinal cord or nerve root compression
- Bladder outlet or urethral obstruction
- Development of new central nervous system (CNS) metastases
- Subjects that develop new CNS metastases in the setting of improving baseline disease may have focal radiation, resection, or other local curative procedures performed after consultation with the Medical Monitor.

If continued study therapy is deemed to offer the subject potential benefit, subjects may be allowed to restart study therapy after recovery from symptoms related to the procedure performed (i.e., local edema) and steroid dosing at < 10 mg prednisone/day or equivalent, after recovery to baseline or grade 1.

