12.1.6. Discontinuation of Subjects from Treatment

Subjects MUST discontinue investigational product (and non-investigational product at the discretion of the investigator) for any of the following reasons:

- Withdrawal of informed consent (subject's decision to withdraw for any reason)
- Any clinical adverse event (AE), laboratory abnormality or intercurrent illness which, in the opinion of the investigator, indicates that continued participation in the study is not in the best interest of the subject
- Pregnancy
- Termination of the study by Sponsor
- Loss of ability to freely provide consent through imprisonment or involuntarily incarceration
- for treatment of either a psychiatric or physical (e.g., infectious disease) illness
- Inability to comply with protocol
- Discretion of the investigator
- Disease progression or clinical deterioration as defined in Section 9.3
- Dosing delays greater than the maximum allowed dosing delays as defined in Section 8.11. All subjects who discontinue should comply with protocol specified follow-up procedures as outlined in Section 12.1.4. The only exception to this requirement is when a subject withdraws consent for all study procedures or loses the ability to consent freely (i.e., is imprisoned or involuntarily incarcerated for the treatment of either a psychiatric or physical illness).

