7.5. Examination of Subgroups

Analysis endpoints of safety and efficacy variables may be further explored with the following subgroups:

- Tumor ratio (1:4, 1:3, 1:2 or dose set by longest diameter formulas)
- Dose schedule (every 2 weeks versus every 4 weeks)
- Superficial tumor injection subjects versus deep tumor injection subjects
- Tumor type (Sarcoma)
- Status of prior treatment with platinum-based antineoplastics or vinca alkaloid therapies
- Subjects with less than 2 tumors injected compared to those with ≥ 2 tumors
- Tumor burden: subjects receiving $\geq 40\%$ of tumor burden injected versus those receiving $< 40\%$; tumor burden is calculated based on EDC documentation of target, bystander, non-target, and new tumors. Subjects receiving $\geq 40\%$ of baseline total tumor burden injected overall (during the course of therapy) and at first dose will be explored. For overall, the sum of all injection volumes will be used in the calculation.

The subgroups to be analyzed for each endpoint are described in Section 8, Section 9, and Section 10.

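### Protocol 14.3.3 breaks DCR down by number of INT230-6 doses, but dose count is partly set by the outcome, so DCR would tend to look higher with more doses even if the drug were inert

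*Protocol*

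**What the plan says.** **The breakdown.** Protocol 14.3.3 makes DCR the primary efficacy endpoint, "defined as the sum of complete, partial and stable disease responses divided by the total number of subjects in the efficacy population". It adds exploratory analyses by cohort grouping and by "tumor types, study visit, number of INT230-6 doses, number of cycles of INT230-6 (i.e., retreatment), and number of prior lines of therapy".

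**When dosing stops.** The Synopsis has induction "followed by maintenance dosing once every 9 weeks +/- 10 days until CR, PD or 2 years, whichever is first". Section 5.2.1 (EC3) continues until CR, "confirmed progression (iCPD) or 2 years whichever is first". Section 12.1.6 lists, among reasons that oblige a subject to stop, "Disease progression or clinical deterioration as defined in Section 9.3". Section 9.3 permits sites to "continue to treat the subject until progression is confirmed and found to be advancing and continuing at the next imaging assessment". The Synopsis and 5.2.1 differ on whether progression must be confirmed, and the sponsor should reconcile them. Under either wording the outcome ends dosing.

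**Retreatment.** Protocol 14.2.6 says that in the escalation cohorts "those subjects who have completed treatment and have not started any subsequent anti-cancer therapy were eligible for retreatment".

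**The SAP.** Section 9 counts progressive disease as clinical or radiological deterioration that leads to the subject coming off treatment, and stable disease as any adequate assessment that is not CR, PR or progression. The subgroup list in 7.5 has neither dose count nor cycle count, but includes "Subjects with less than 2 tumors injected compared to those with ≥ 2 tumors" without saying when tumors are counted. Section 6.7 describes the three retreated subjects as a case series, with no aggregate table solely for them. Section 13 reports no changes from the protocol's methods.

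**The concern.** A subgroup comparison is interpretable when group membership is fixed before the outcome can act on it. Number of doses is not. A subject who deteriorates during induction stops with few doses and, under the response-evaluable definition, stays in the denominator as a failure. A subject on the fixed-dose schedule reaches dose 6 only by not being taken off around the 12-week scan.

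A table of DCR by dose count therefore mixes two explanations: more doses control disease, and controlled disease allows more doses. It would look like a dose-response on the main efficacy measure. Neither document provides a landmark, a time-dependent exposure analysis or a caution on interpretation.

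**Working it through.** The plan gives no figure for DCR by dose count. Its only numerical design figures are 90% intervals for 16 subjects. Those in Protocol 14.1 for 3, 4 and 5 responders reproduce as exact intervals (5.3–41.7%, 9.0–48.4%, 13.2–54.8%) but do not bear on this point. The check asks what the table would show for a drug with no effect.

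**Inputs from the documents**
- Induction doses on Days 0, 14, 28, 42 and 56 (Protocol 12.1.3.1).
- Maintenance every 9 weeks (Protocol 5.2.1), so dose 6 is due on Day 56 + 63 = 119.
- First scan at 12 weeks, Day 84, then every 9 weeks (footnote 10 to the schedules; SAP 4.4).
- Confirmation of progression 4 to 8 weeks after it is first seen (Protocol 18.1.2).

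**Assumptions not in the documents**
- Exponential time to progression, unaffected by dosing, median 3 months (91.3 days).
- 30% of progressions stop dosing clinically when they occur. The other 70% are found at the next scan and dosed until confirmation, uniformly 28–56 days later.
- Stopping for other reasons at a rate of 5% per month.
- Disease control means progression-free at Day 84, with everyone scanned.

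**Formulas**
- S(t) = exp(−ln2 × t/91.3): S(56) = 0.6537, S(84) = 0.5285, S(119) = 0.4052.
- Not stopped for other reasons, G(t) = exp(−0.05 × t/30.4375): G(56) = 0.9121, G(119) = 0.8224.
- Progression found at Day 84 is confirmed between Days 112 and 140, so the chance of still being dosed at Day 119 is (140 − 119)/28 = 0.75.

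**≥6 doses**
- Controlled: 0.8224 × (0.7 × 0.5285 + 0.3 × 0.4052) = 0.4043
- Not controlled: 0.7 × 0.4715 × 0.75 × 0.8224 = 0.2036
- DCR = 0.4043/0.6079 = 66.5%

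**≤4 doses**
- Controlled: 0.5285 × (1 − 0.9121) = 0.0465
- Not controlled: 0.7 × 0.4715 × 0.0879 + 0.3 × [0.4715 − (0.6537 − 0.5285) × 0.9121] = 0.0290 + 0.1072 = 0.1362
- DCR = 0.0465/0.1827 = 25.4%

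**Exactly 5 doses** (the remainder)
- Controlled 0.0778, not controlled 0.1317; DCR = 37.1%

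Overall DCR is 52.9%. A simulation of the same model gives the same results, and varying the two main assumptions gives:

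| Median (months) | Progressions that stop dosing clinically | DCR, ≤4 / 5 / ≥6 doses |
|---|---|---|
| 2 | 30% | 16% / 28% / 52% |
| 3 | 0% | 53% / 25% / 60% |
| 3 | 30% | 25% / 37% / 67% |
| 3 | 60% | 17% / 47% / 76% |
| 3 | 100% | 12% / 57% / 100% |
| 6 | 30% | 46% / 53% / 83% |

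The rise is monotone in all 12 scenarios with some clinical stopping (medians 2, 3, 4 and 6 months; shares 30%, 60% and 100%). With none it is not, although ≥6 doses remains highest. If subjects off treatment before week 12 are then counted as not controlled, the 3-month row becomes 0% / 14% / 60%.

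**Check of the remedy.** Among subjects progression-free at Day 84, the chance of remaining so at Day 147 is exp(−ln2 × 63/91.3) = 62.0% whatever the earlier dose count. The simulation gives 62.1% with ≤4 doses by Day 84 and 62.3% with 5. The landmark removes the artefact.

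**The case against.** **The SAP may never produce this table.** Protocol 14.3 defers to the SAP, SAP 7.5 does not list dose count, and SAP 6.7 already limits retreatment to a case series. This largely stands for retreatment. For dose count it leaves a gap, because SAP 13 declares no departure from the protocol and the breakdown is still formally planned.

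**Dosing is not conditional on disease control at every step.** It may run through unconfirmed progression, and in the 14-day cohorts all five induction doses precede the first scheduled scan. This stands. Within induction the link works through clinical stopping, which is why the gradient depends on how common that is. Stopping at CR pulls slightly the other way.

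**The model's endpoint is simpler than the plan's.** The SAP uses best overall response, and Protocol 12.2.1 has injected tumors evaluated at every visit, so an early stopper is not automatically a failure. A reader might infer that DCR must be 0% below five doses and 100% from six. The documents do not support that: it needs dosing to end exactly at progression, no other reason for stopping and a Day 84 endpoint. At the dose-6 end, however, SAP section 9 strengthens the link: a subject with an adequate 12-week assessment who is still on treatment is not progressive by definition.

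**The Scan Evaluable Population helps.** Requiring a scan at two months or later removes many early stoppers, but not the selection at dose 6.

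**The model covers only part of the trial.** Planned maintenance exists only in EC3, DEC2 and FEC, so these percentages do not describe the escalation cohorts.

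**The injected-tumors subgroup.** A reader might infer that it has the same fault. That holds only if tumors are counted over the whole course, which SAP 7.5 does not specify. Tumor number also reflects baseline disease extent.

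**Conclusion.** The concern holds in a limited form. Dose count is partly determined by disease control, so the Protocol 14.3.3 breakdown cannot be read as a dose-response. Under the stated assumptions an inert drug gives about 25%, 37% and 67% across ≤4, 5 and ≥6 doses. The direction is stable wherever some progressions stop dosing clinically. Without clinical stopping, only the excess at ≥6 doses remains.

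A reader might go further and conclude that the trial's efficacy result is invalid or that a spurious significance test is planned. The documents do not support either: the breakdown is labelled exploratory, no test is stated for it, and the primary objective is safety. The stated hypotheses concern control of disease, loading ratio and the share of disease treated, not number of doses. The change is still worth making, because the table would mislead and nothing in the SAP withdraws it.

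**What to change.** - In Protocol 14.3.3, remove number of INT230-6 doses and number of cycles (retreatment) as breakdowns of DCR. Report both as exposure only.
- If a dose-response look is wanted, group by variables fixed at first dose (cohort, loading ratio, volume given at Cycle 1 Day 0). Alternatively, use a landmark at the first scan: subjects still event-free then, grouped by doses received up to then, with only later outcomes counted.
- Record the removal in SAP 13.
- If the subgroup of fewer than 2 versus at least 2 injected tumors is kept in SAP 7.5, count tumors at the first dosing session.

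The cost is wording in two documents and no new data. One exploratory table is lost, or replaced by a landmark table with fewer subjects.
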